The consent must be agreed, dated and signed by the patient before any study-related procedure starts.

The consent form is made in duplicate: the original copy is kept by the Investigator and one copy is given to the patient.

If any information becomes available during the trial that may be relevant to the patient's willingness to keep on participating in the trial, an updated written informed consent must be submitted to the patient to confirm his/her agreement to continue participating.

XIII.6 - CONSEIL NATIONAL DE L'ORDRE DES MEDECINS (CNOM)

A separate financial agreement will be signed between the sponsor and the investigator and/or the institution involved.

According to French national law (article R1121-3-1 du Code de la Santé Publique), the financial agreement related to the study will be submitted for information to the CNOM upon financial agreement signature.

According to French national law (article L.4113.6 du Code de la Santé Publique), the Sponsor will inform the CNOM of the agreement implementation.

According to the 2011-2012 French law dated December 29, 2011 and its implementing decree 2013-414 of 21 May 2013, the sponsor will publish the existence of this agreement, as well as benefits in kind or in cash provided directly or indirectly to the Investigator.

XIII.7 - PROTOCOL AMENDMENT

Neither the Investigator nor the Sponsor may alter the protocol without the authorization of the other party. Any amendment that may be issued, must be dated and signed by both parties and must appear as an amendment to the protocol before implementation.

Substantial amendments are submitted for authorization to Competent Authority (CA) and approval to EC before implementation.

Substantial amendments on safety measures are submitted for approval/authorization to EC and CA but could be implemented immediately under specific conditions defined with the sponsor.

XIII.8 - Use of Information and Publication of Study results

The study data and study results are the exclusive property of the Sponsor. Nevertheless, the sponsor is aware that its property rights over the data must not prevent the investigator from communicating the study

results to the scientific community. Provided any such presentations do not prevent recognition of its industrial property rights, the Sponsor therefore authorises the investigator to draw up and present any scientific papers concerning the study after having received the written Sponsor authorization.

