- at patient home for t:slim X2 Insulin Pump with Control-IQ Technology and/or Dexcom G6 CGM refreshing trainings (initiation and follow-up periods), at D3 (ideally at the time of the 1st bolus following the hospital discharge of the run-in period), at D9, D30, D60 and any time the patient requires it.

In the investigational group, and specific to the study for safety purpose, the Tandem Pump with ControllQ Technology system data are uploaded to the t:connect® platform twice daily at 6 hours minimum interval during the first week (Day 3 to Day 9) by the family nurse (if the patient/caregiver is not able to do it) to allow the investigator to closely monitor the patient.

In the control group:

- at patient home for CGM trainings, at selection and follow-up (at D70) periods.

In addition, **for both study groups**, the HHP is present at the hospital for the study end planned at D90 as detailed in section VI.6.

V.3 - COMPARATOR INTERVENTION

In the control group, patients continue to receive their usual care which will be composed, according to the investigator's prescription, of basal-bolus multiple daily injection insulin treatment and glycaemic controls performed by family nurse during usual daily home visit(s).

In addition, glucose will be monitored through a Dexcom G6 CGM for 14 days at the selection period and for 20 days (to ensure exhaustive data capture for at least 14 days) at the follow-up period ending. The initial 14-day monitoring period can be extended by an additional 14-day selection period in case of missing CGM data points (corresponding to less than 70% of the data points available over the 1st CGM recording as per inclusion criterion detailed in section IV.1.2).

V.4 - Use of the investigational medical device

The automated insulin delivery system is to be used according to instructions given during the investigators, family nurses and patients training sessions. Knowledge assessment will be performed at the end of each training session.

All referring study sponsor and representative personnel, as well as the home healthcare providers nurses involved in the CLOSE AP+ trial will be trained to the automated insulin delivery system use and management before the study start.

Investigators have to refer to user guide of medical devices used in the clinical trial regarding contraindications, warnings and precautions.

V.4.1 - MANAGEMENT AND DISPENSING OF MEDICAL DEVICE

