- For patients randomized to the control group: o The Dexcom G6 sensor will be removed and other parts i.e., receiver and transmitter, collected.
 - The patient will be reminded of the installation of a CGM for 20 days at Day 70.
 The patient will be provided with the schedule of visits at home and at the hospital, with the patient diary
- For patients randomized in the investigational group: Pump will be installed.
 - Patient visit will include 2 nights at hospital for patient observation following the set-up of the Dexcom G6 CGM system with the Pump in open mode.
 - The patient (and the caregiver if applicable) will be trained to the use of the Pump and CGM in open mode, specifically on the management of alarms or alerts on the pump and on meal information entry into the pump for bolus insulin delivery (always the same value to facilitate the entry and avoid carbohydrate calculation). Patients will be provided with a short notice describing the management of meals announcement before leaving hospital.
 - After 48h of observation, the Investigator will ensure that the patient (or the caregiver) is able to go back home and follow the instructions for study continuation, and plan the date of the next visit at the hospital to initiate the

Run-in period. Otherwise, the patient will be withdrawn from the study and replaced.

- The patient will be reminded of the next steps of the protocol and will be provided with the schedule of visits at home and at the hospital, with the patient diary
- The investigator will fill in the e-CRF.
- During the next weeks, the investigator will have access to patient's glycaemic data through the cloud-based t:connect® platform and will be trained by the HHP to the display and exploitation of data on the t:connect® platform. The investigator will receive the report from the HHP following his/her visit at patient home.
- o After Visit 1, the investigator will complete the e-CRF

VI.3.2 - ROLES OF THE HOME HEALTHCARE PROVIDER (HHP)

Patients randomized in the control group:

- The HHP will attend the visit at the hospital to collect the Dexcom G6 CGM devices, the dedicated laptop and fill the related certificate.
- The HHP will contact the family nurse to plan the date for the installation of the Dexcom G6 CGM system at Day 70 at the patient's home.
- The HHP will remind the patient to report adverse events and/or device deficiencies/failure in the patient diary.

Patients randomized in the investigational group:

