- Twenty days before the study end (D70, visit 8), a new Dexcom G6 CGM system provided by the HHP will be installed for a 20-day continuous glycaemia recording period. During Visit 8, in addition to usual care, the family nurse will:
 - o Install the new blinded Dexcom G6 CGM system,
 - Be trained by the HHP to the procedure of data upload and data visualisation on the CLARITY® platform,
 - o Be reminded by the HHP on the precautions to use the Dexcom G6 CGM system and on the procedures in case of emergency or technical issues.

VI.6 - END OF STUDY VISIT (V9)

The end of study visit will be performed at the hospital to unequip and remove the devices, and perform the evaluations required by the protocol. All patient materials will be collected and the patient will be switched back to MDI T2D care as per investigator's prescription.

VI.6.1 - ROLES OF THE INVESTIGATOR

At the end of study visit, the Investigator will:

- Remove the Dexcom G6 CGM (for every patient) and the Tandem t:slim X2 Insulin Pump (for patients
 of the investigational group only). Before removing the devices, the Investigator will ensure that data
 have been collected by the HHP.
- Perform the following evaluations:
 - Adverse events and device deficiencies/failure.
 - Concomitant medications.
 - Physical examination, blood pressure and body weight.
 - Laboratory data: HbA1c, blood glucose, total cholesterol, triglycerides, HDL-Cholesterol, LDL-Cholesterol, serum albumin, AST, ALT, gamma GT and serum Creatinine, blood counts (Red Blood Cells (RBC), White Blood Cells (WBC), platelets, haemoglobin, hematocrit) with their sampling date, fasting status, unit and normal range in use.

| - | Collect | , the patient diary and study documentation. |
|---|---------|--|
| | | |
| | | |
| | | |

VI.6.2 - ROLES OF THE HOME HEALTHCARE PROVIDER (HHP)

The HHP will attend the end of study visit at the hospital to:

- Upload data from the Dexcom G6 receiver to the CLARITY® platform for patients of the control group, and data from the Tandem t:slim X2 Insulin Pump to the t:connect® platform for patients of the investigational group,
- Collect and return Dexcom G6 CGM, Tandem t:slim X2 Insulin Pump devices and dedicated laptop (as detailed in section V.4).

VI.6.3 - ROLES OF THE FAMILY NURSE

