 Blood counts (Red Blood Cells (RBC), White Blood Cells (WBC), platelets, haemoglobin, and hematocrit).

VI.7.1.8 - GLYCAEMIC CONTROL AND GLYCAEMIC VARIABILITY

In addition to HbA1c assays, the glycaemic control and variability will be computed based on the continuous measurement of the glucose values recorded after wearing the CGM device in blinded mode during the 14 consecutive days of the selection period and every day from D70 to D90.

VI.7.1.9 - Adverse Events/Device Deficiencies/Failure

Safety assessments will consist in evaluating all serious and non-serious adverse events (AE), and device deficiencies/failure occurring from the Informed Consent Form (ICF) signature until the end of the study.

At each visit, occurrence of AEs and device deficiencies/failure should be inquired and follow-up of previously reported AEs and device deficiencies/failure should be performed. Related essential data should be recorded in the patient's medical file and in the e-CRF by the Investigator.

For the AEs, the following data will be recorded in the e-CRF:

[figure not shown]
- Description of the AE
- Seriousness of the event
- Onset and resolution dates of the AE
- Severity of the AE (mild, moderate or severe)
- Causality with regards to IMD
- Causality with regards to investigation procedures
- Action(s) taken regarding the IMD Corrective treatment/therapy given Event outcome.

In addition, the following parameters will be considered for assessment of the safety profile of automated insulin delivery system:

[figure not shown]
- Hypoglycaemic events defined as at least 10 min of continuous CGM readings below the thresholds of (1) 70 mg/dL (3.9 mmol/L) or (2) 54 mg/dL (3.0 mmol/L),
- Non severe hypoglycaemic events, being defined by CGM readings between < 70 mg/dL (3.9 mmol/L) and ≥ 54 mg/dL (3.0 mmol/L),
- Severe hypoglycaemic events being defined by CGM readings < 54 mg/dL,
- Severe hypoglycaemic events requiring third party assistance,
- Severe hypoglycaemic events requiring hospitalization,
- Severe hyperglycaemic events being defined by CGM readings ≥ 300 mg/dL for over 1 hour, Device incidents and deficiencies.

A Data Safety Monitoring Board (DSMB) will review the safety data of the five first patients of each group, then 25 patients having completed the study, and more frequently if judged necessary by the DSMB.

[figure not shown]

[figure not shown]

VII - ENDPOINTS

VII.1 - PRIMARY ENDPOINT

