- Absolute change of Time In Range from the 14 days completed CGM recording at the end of the selection period (baseline) to the last 14 days completed CGM recording from D70 to D90 at the end of the study period: time in range is defined in section VII.1 as the percentage of time spent in target range of glucose level (CGM measurements in 70-180 mg/dL (including boundaries)). At baseline, as well as from D70 to D90, any day of the considered period need to have ≥ 70% non missing data points to be eligible for the TIR computation. The absolute change in TIR from Baseline, i.e., D90-D0 will be calculated 3 times for each patient: (1) for the full 24-h day, (2) for the diurnal period (from

[figure not shown]

06.00 H to 23.59 H) and (3) for the nocturnal period (from 00.00 H to 05.59 H),

- Time below target range is defined as the percentage of time spent with CGM glucose measurements (1) <70 mg/dL, and (2) <54 mg/dL, during the last 14-day CGM completed recording from days 70 to 90. The time below target range will be computed for the full 24-h day, the diurnal period (from 06.00 H to 23.59 H) and the nocturnal period (from 00.00 H to 05.59 H) separately,
- Time above target range is defined as the percentage of time spent with CGM glucose measurements (1) >180 mg/dL, and (2) ≥250 mg/dL, during the last 14-day CGM completed recording from days 70 to 90. The time above target range will be computed for the full 24-h day, the diurnal period (from 06.00 H to 23.59 H) and the nocturnal period (from 00.00 H to 05.59 H) separately,
- Total daily insulin dose change from baseline to D90 (sum of basal and bolus insulin injection), Body weight absolute change from baseline (end of period of selection) to D90.

VII.3.1 - SAFETY PARAMETERS

Safety assessments are detailed in section VI.7.1.9. They include:

- Number of diabetes-related hospital admissions and their length of stay: the frequency of scheduled and unscheduled diabetes-related hospital admissions will be calculated for each study patient from baseline to D90.
- Number of hypoglycaemic events
- Number of diurnal hypoglycaemic events (i.e., occurring from 06.00 H to 23.59 H)
- Number of nocturnal hypoglycaemic events (i.e., occurring from 00.00 H to 05.59 H)
- Number of non severe hypoglycaemic events
- Number of severe hypoglycaemic events
- Number of severe diurnal hypoglycaemic events (i.e., occurring from 06.00 H to 23.59 H)

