Each secondary efficacy endpoint will be summarised at each time point using descriptive statistics and compared between study groups using Cochran-Mantel-Haenszel chi-squared tests adjusted on the HbA1c level at baseline (2-categories stratification variable) or analyses of covariance with or without repeated measures (depending on the analysed parameter and its frequency of collection in both study groups) adjusted on the HbA1c level at baseline.

When appropriate, analyses based on CGM measures will be performed considering (1) the full 24-h day, (2) diurnal period (from 06.00 H to 23.59 H) and (3) nocturnal period (from 00.00 H to 05.59 H) separately.

When relevant, continuous, longitudinal endpoint data (e.g. HbA1c, Total daily insulin dose, body weight) will be analysed using the mixed effects model for repeated measures method based on the restricted maximum

likelihood for estimation with several prespecified fixed effects, including first-order interactions with time, and the corresponding endpoint as the dependent variable in the model. ANCOVA will be used for analyses of measures taken at a single time point post baseline in both study groups.

X.3.5 - SAFETY EVALUATION

Safety data will be tabulated descriptively by study group and assessment time, when relevant. Extent of exposure and Adverse Events will be tabulated in the Randomised ITT and the safety data sets (defined in section X.2.1). No statistical test will be performed.

X.3.5.1 - EXTENT OF EXPOSURE

Duration of the 4 study periods (Selection, Initiation, Run-in and Follow-up periods) and overall study duration will be tabulated (expressed in days) by study group (and globally), as both quantitative and categorical data.

Overall study duration is defined as the time interval between the actual date of the selection visit (*VO included*) and the actual date of the end of study visit (*V9 excluded*) whether the end of study occurred at the time of premature withdrawal or on visit date corresponding to D90 as planned, i.e., as the time interval equal to "date of end of study visit (V9) - date of selection visit (V0)".

X.3.5.2 - ADVERSE EVENTS (AES)

The time period for the recording of Adverse Events (AEs) is the time interval between selection (V0) and end of study (V9) divided in 2 periods, either before or after the initiation visit (V1). All reported AEs will be classified in one of these 2 periods, according to their start date.

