AEs tabulated evaluations described below will be performed on Study Emergent Adverse Events (SEAEs). AEs occurring before the initiation visit (V1) will be tabulated in the Randomised ITT and the safety data sets separately, if relevant, or they will be listed if too few patients are concerned.

Each AE (whether serious or not serious, according to their regulatory definition provided in section VIII.1) having been reported throughout the study for a given patient will be classified by Preferred Term (PT) and corresponding primary System Organ Class (SOC), using the MedDRA terminology, prior to the study database lock.

An AE will be categorised as Study Emergent if it begins at the earliest on the day of the initiation visit (V1). In case of missing or partial AE start date, an AE will be considered as Study Emergent (SE):

- (1) if the AE start date is unknown,
- or (2) if the partial AE start date is on or after the date of the initiation visit (V1) (i.e., 'year' or 'year and month' is/are 'the same as' or 'after' those of the date of Visit 1).

An overall summary of AEs will be provided by study group, including:

- the number and percentage of patients with at least 1 AE and the total number of AEs,
- the number and percentage of patients with at least 1 SEAE and the total number of SEAEs,
- the distribution of the number of SEAEs reported by patient (in 5 categories, if relevant: 1 SEAE, [2 3] SEAEs, [4 6] SEAEs, [7 9] SEAEs or 10 or more SEAEs),
- the number and percentage of patients with at least 1 Serious SEAE and the total number of Serious SEAEs,

- the number and percentage of patients with at least 1 possibly IMD related SEAE (possibly IMD related SEAEs being defined as SEAEs for which the investigator has reported at least once either 'Causal relationship' or 'Probable' or 'Possible' for the relationship to the IMD) and the total number of those possibly IMD related SEAEs,
- the number and percentage of patients with at least 1 SEAE possibly related to investigation procedures (SEAEs possibly related to investigation procedures being defined as SEAEs for which the investigator has reported at least once either 'Causal relationship' or 'Probable' or 'Possible' for the relationship to the investigation procedures) and the total number of those SEAEs possibly related to investigation procedures,
- the number and percentage of patients with at least 1 AE leading to study premature withdrawal and the total number of those significant AEs.

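### CGM-defined hypo- and hyperglycaemic events are raw numbers with no visible counting window or wear denominator, although planned post-V1 CGM wear matches between groups only in D70-D90 (minor)

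*Combined protocol and SAP*

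**What the plan says.** **Events.** Section VI.7.1.9 gives "Hypoglycaemic events defined as at least 10 min of continuous CGM readings below the thresholds" of 70 or 54 mg/dL. It defines severe hypoglycaemia by CGM readings below 54 mg/dL, and severe hyperglycaemia by readings of at least 300 mg/dL for more than 1 hour. Section VII.3.1 lists these in the form "Number of non severe hypoglycaemic events", with diurnal and nocturnal splits for some.

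**Windows given for other things.**
- Section VI.7.1.8 computes glycaemic control and variability from CGM worn "during the 14 consecutive days of the selection period and every day from D70 to D90".
- Section VII.2.1 ties time below and above range to the last 14 days of recording in D70-D90.
- Section VI.7.1.9 collects adverse events and device deficiencies from consent to study end. The CGM events follow as additional parameters.
- Section X.3.5.2 splits adverse events at V1.

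None of these is stated to apply to the CGM-defined events. The exposure table in X.3.5.1 gives durations of study periods, not CGM wear.

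**CGM wear.** For control patients at V1 (VI.3.1), "The Dexcom G6 sensor will be removed and other parts i.e., receiver and transmitter, collected". CGM returns "for 20 days (to ensure exhaustive data capture for at least 14 days) at the follow-up period ending" (V.3); at D70 a new system "will be installed for a 20-day continuous glycaemia recording period" (VI.5.3). Investigational patients wear CGM through open mode and closed loop to D90 (V.1.2, VI.3, VI.3.3, VI.5.3).

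**Admissions.** Section VII.3.1 counts diabetes-related admissions, both scheduled and unplanned, from baseline to D90, with length of stay. Sections VI.3.1 and VI.4 give investigational patients only a 2-night stay at initiation and another at run-in.

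**The concern.** A count of threshold crossings depends on how long the sensor is worn. In this design the investigational group is observed by CGM for several times as long as control, unless counting is confined to D70-D90. Section X.3.5 tabulates safety data by study group. A raw-count table over a longer window would mix the effect of the strategy with observation time, in the direction that makes closed loop look less safe. The stated aim (Synopsis, I.3) concerns the rate of acute metabolic complications, whereas the listed endpoints are numbers.

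The admissions count raises a similar, smaller issue. Read literally, it includes hospital nights that the protocol itself imposes on one group only.

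**Working it through.** **Check on the plan's own figure.** V.6 gives about 15 weeks from V1 to V9 in the investigational group. Open mode lasts 14 days (VI.3) and D0 to D90 is 90 days: 14 + 90 = 104 days, and 104/7 = 14.9 weeks. If the 48 h observation is counted on top, 16 + 90 = 106 days = 15.1 weeks. Both agree with the plan.

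**Planned CGM wear by candidate window.** Inputs are 14 to 28 selection days in both groups (VI.2), 14 open-mode days, 90 days from D0, and 20 control days from D70.

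| Window | Investigational (days) | Control (days) | Ratio |
|---|---|---|---|
| Consent to D90, 14 selection days | 14 + 14 + 90 = 118 | 14 + 20 = 34 | 3.5 |
| Consent to D90, 28 selection days | 28 + 14 + 90 = 132 | 28 + 20 = 48 | 2.75 |
| V1 to D90 | 14 + 90 = 104 | 20 | 5.2 |
| V1 to D90, 48 h added | 16 + 90 = 106 | 20 | 5.3 |
| D0 to D90 | 90 | 20 | 4.5 |
| D70 to D90 | 20 | 20 | 1.0 |

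At equal true event rates, the ratio of expected raw counts equals the wear ratio, whatever the rate. The consent rows also assume the same rate during selection.

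**What a real benefit would look like, counting from V1.** A true halving of the rate gives a raw count ratio of 0.5 × 5.2 = 2.6. Raw counts would be equal only at a true rate ratio of 20/104 = 0.19, a reduction of 81%.

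**Admissions per investigational patient completing both stays.**
- Counted from the end of selection or from V1: 2 stays, 4 nights. For 21 to 28 patients this is 42 to 56 stays and 84 to 112 nights.
- Counted from investigational D0, which is the run-in visit in Figure 2A: 1 stay, 2 nights.
- Control: 0 in either case.

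**The case against.** **The window may be D70-D90 after all.** VI.7.1.8 stands directly before the event definitions and names selection and D70-D90. If it governs the events, wear is matched and nothing is distorted. This reading is possible, but VI.7.1.8 speaks of glycaemic control and variability, and the events appear in the next section without a window.

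**The 5.2-fold figure is conditional.** This stands. A reader might infer that the plan will show five times as many investigational events. The documents do not support that: the V1 split in X.3.5.2 is for adverse events, and the plan does not say that CGM events are counted from V1. From consent the ratio is 2.75 to 3.5. X.3.5 also allows tabulation by assessment time where relevant, which could separate the periods.

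**Little depends on these tables.** This also stands. X.3.1 makes all results beyond the primary analysis exploratory and descriptive, and X.3.5 excludes safety tests. Time below and above range gives a matched CGM comparison, and events needing third-party assistance or hospitalisation can be ascertained without CGM.

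**The DSMB.** A reader might infer that its reviews would be misled by unequal wear. The plan does not say at what follow-up or in what form the board sees these events, and its role and meetings are set out in a separate charter. No figure can be attached to this.

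**Removed text.** Parts of the endpoint and analysis sections are not visible and could contain a rule. The point is therefore confined to the visible endpoint wording.

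**Admissions.** Counting scheduled stays may be intended, since healthcare costs are among the study's aims. X.3.5.2 lists and tabulates unplanned hospitalisations separately. That helps only in part, because the table covers all causes and leaves the VII.3.1 endpoint as it is. On the start point, the safety sections use V1 as baseline for laboratory values and blood pressure (X.3.5.3, X.3.5.4), which favours V1, but nothing says so for admissions.

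**Conclusion.** The concern holds as a minor point. The visible text fixes neither a window nor a denominator for the CGM-defined events, and planned wear is unequal in any between-group window that takes in the time from V1 to D70. If raw counts are tabulated by group over the windows from consent, V1 or D0, equal true rates would show about 2.75 to 5.2 times as many investigational events (5.3 if the 48 h observation is counted separately). In D70-D90 the ratio is 1.0.

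These figures rest on planned wear with full adherence and on the same event rate in both groups. VI.2.2 leaves the selection sensor in place until V1, which would lengthen wear in both groups and lower the consent-based ratios somewhat. The primary analysis and the time-in-range family are not affected, no test is involved, and no conclusion about bias in the efficacy result follows.

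The admissions issue is secondary: 2 stays and 4 nights per investigational completer if counted from V1, or 1 stay and 2 nights from investigational D0, against none in control.

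**What to change.** In VII.3.1 and the SAP:

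1. Report CGM-defined hypo- and hyperglycaemic events per patient-week of valid CGM wear.
2. For the between-group presentation, use the eligible D70-D90 days in both groups, and state whether the VI.7.1.8 window applies to these events.
3. Show investigational events before D70 as a separate descriptive rate, so that early closed-loop safety stays visible.
4. In the admissions endpoint, put protocol-required stays on a separate line and name the visit at which counting starts.

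The wording should be settled now: X.3 has the final SAP approved only after the data review meeting, in an open-label trial.

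The cost is some endpoint and SAP wording, one denominator and one extra table line. No new data are needed, since CGM and pump recordings for the whole participation period already go to the study database (IX.2). The downside is that the between-group comparison uses only 14 to 20 of about 104 investigational post-V1 wear days (14/104 = 13% to 20/104 = 19%), which is why the separate earlier rate is needed.
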